7.2.2.2. Summaries of Laboratory Abnormalities

Laboratory data that are categorical will be summarized using the number and percentage of subjects in the study with the given response at baseline and each scheduled postbaseline visit.

The following summaries (number and percentage of subjects) for treatment-emergent laboratory abnormalities will be provided by lab test and treatment group; subjects will be categorized according to the most severe postbaseline abnormality grade for a given lab test:

- Graded laboratory abnormalities
- Grade 3 or 4 laboratory abnormalities

For all summaries of laboratory abnormalities, the denominator is the number of subjects with nonmissing postbaseline values up to 30 days after last dosing date.

A by-subject listing of treatment-emergent Grade 3 or 4 laboratory abnormalities will be provided by unique subject ID number and visit in chronological order. This listing will include all test results that were collected throughout the study for the lab test of interest, with all applicable severity grades or abnormal flags displayed.

7.3. Body Weight, Height, and Vital Signs

Vital signs (systolic and diastolic blood pressure [mmHg], pulse [beats/min]) at each visit, and change from baseline at each visit will be summarized for the safety analysis set by treatment group using descriptive statistics (n, mean, SD, median, Q1, Q3, minimum, and maximum). The baseline value will be defined as the last available value collected on or prior to the date/time of first dose of study drug. Change from baseline to a postbaseline visit will be defined as the postbaseline value minus the baseline value.

In the case of multiple values in an analysis window, data will be selected for analysis as described in Section 3.7.3. No inferential statistics will be generated.

A by-subject listing of vital signs (systolic and diastolic blood pressure [mmHg], pulse [beats/min], respiration [breaths/min], and body temperature [°C]) will be provided by subject ID number and visit in chronological order. In the same manner, a by-subject listing of body weight, height, and BMI will be provided separately.

7.4. Prior and Concomitant Medications

Medications collected at screening and during the study will be coded using the current version of the World Health Organization (WHO) Drug dictionary. The medications will be categorized as prior, concomitant, or both using the following definitions:

- Prior medications: any medications taken and stopped prior to or on the date of first study drug administration
- Concomitant medications: any medications initially taken on or after the initial study drug dosing date and within the study drug treatment period (including the study drug therapeutic reach)

Concomitant medications will be summarized by preferred name using the number and percentage of subjects for each treatment group. A subject reporting the same medication more than once will be counted only once when calculating the number and percentage of subjects who received that medication. The summary of concomitant medications will be ordered by descending frequency of preferred names. For drugs with the same frequency, sorting will be done alphabetically. Summaries will be based on the Safety Analysis Set. No inferential statistics will be generated.

For purposes of analysis, any medication with a stop date that is on or prior to the initial study drug dosing date or start date that is after the last study drug dosing date will be excluded from a concomitant medication summary. If a partial stop date is entered, any medication with the month and year (if day is missing) or year (if day and month are missing) prior to the initial study drug dosing date will be excluded from the concomitant medication summary. If a partial start date is entered, then any medication with the month and year (if day is missing) or year (if day and month are missing) after the study drug stop date will be excluded from the concomitant medication summary. Medications with completely missing dates will be included in the concomitant medication summary.

All prior and concomitant medications (other than per-protocol study drugs) will be provided in a by-subject listing sorted by subject ID number and administration date in chronological order.

7.5. Electrocardiogram Results

A Shift table of the investigator's assessment of ECG results at baseline (normal, abnormal but not clinically significant, abnormal and clinically significant, or missing) versus the investigator's assessment at each on-treatment visit (normal, abnormal but not clinically significant, abnormal and clinically significant, or missing) will be presented by treatment group. The number and percent of subjects in each cross-classification group will be presented (subjects with a missing value at baseline or on-treatment visit will not be included in the denominator for percent calculation).

A listing of ECG results including comments regarding clinically significant abnormalities will be provided.

7.6. Other Safety Measures

A data listing will be provided for subjects who become pregnant during the study.

7.7. Changes From Protocol-Specified Safety Analyses

There are no deviations from the protocol-specified safety analyses.

8. PHARMACOKINETIC ANALYSES

8.1. Pharmacokinetic Sample Collection

A single PK blood sample will be collected at Weeks 2, 4, 8, 12, and Early Termination (if applicable) for all subjects.

CCI

█

CCI

8.3. Population PK Analysis

The population PK models for SOF, GS-331007, VEL, and VOX (as applicable) previously developed for regulatory submission (SOF/VEL US NDA and SOF/VEL/VOX US NDA) will be applied to the data collected from CCI sparse CCI PK sampling of this study. PK parameters (AUC_{τ} and C_{\max} for SOF and GS-331007, and AUC_{τ} , C_{\max} , C_{\min} or C_{τ} for VEL and VOX) will be estimated from the simulated SOF, GS-331007, VEL, and VOX concentration data using the respective population PK models, for all subjects in the PK Analysis Set. The population PK model-derived PK parameters will be listed and summarized by treatment group.

The population PK parameters of SOF, GS-331007, VEL, and VOX (as applicable) will be compared to the population PK parameters in the corresponding US NDA population to assess the difference in PK exposure between Korean subjects in this study and the overall population. The statistical model will include population group as a fixed effect. The following SAS[®] PROC MIXED code will provide the comparison between the population groups and the 90% CI calculations for natural log-transformed PK parameters.

```
proc mixed data poppk method type3;  
  where analyte '{GS-XXXX}' and param '{AUCtau}';  
  class popgrp;  
  model logval popgrp;  
  lsmeans popgrp / diff;  
  estimate "Korea vs USNDA" popgrp 1 -1 / cl alpha 0.1;  
  ods output Estimates LS_Diffs LSMeans LS_Means CovParms MSE;  
run;
```

The estimate statement will be used to produce the point estimate and the corresponding 90% CI of the difference in PK parameters of interest on a logarithmic scale. The test-to-reference ratio and associated 90% CI will be calculated by taking the exponential of the point estimate and the corresponding lower and upper limits, which is consistent with the two 1-sided tests approach {U.S. Department of Health and Human Services Food and Drug Administration Center for Drug Evaluation and Research (CDER) 2003}, {U.S. Department of Health and Human Services Food and Drug Administration Center for Drug Evaluation and Research (CDER) 2001}.

The following tables will be provided:

- Individual and Summary of Population PK Model-derived PK Parameters by Treatment Group
- Summary of Population PK Parameters for SOF/VEL Treated Subjects in Study GS-US-342-5532 Compared to the SOF/VEL US NDA Population
- Summary of Population PK Parameters for SOF/VEL/VOX Treated Subjects in Study GS-US-342-5532 Compared to the SOF/VEL/VOX US NDA Population

The following listings will be provided:

- Population PK model derived PK parameters

A population PK report based on data from this and possibly other studies will be prepared by the PK scientist.

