3.1.4. Pharmacokinetic (PK) Analysis Set

The PK Analysis Set will include all enrolled subjects who took at least 1 dose of study drug and have at least 1 nonmissing concentration value for the corresponding analyte in plasma. This is the primary analysis set for all PK analyses. The analytes of interest may include SOF (and its metabolites GS-566500 and GS-331007), VEL or VOX where applicable. Within the PK Analysis Set, those subjects with PK exposure data successfully derived from the population PK modeling will be included in the analyses related to PK exposure.

CCI

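### The Korea/NDA exposure ratio in SAP 8.3 can be attenuated toward 1 if it rests on individual estimates from sparse samples under the NDA models; the SAP states no estimator, Korean term or shrinkage limit

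*SAP*

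**What the plan says.** SAP 8.3 takes population PK models "previously developed for regulatory submission (SOF/VEL US NDA and SOF/VEL/VOX US NDA) will be applied to the data collected" in this study. The exposure parameters "will be estimated from the simulated SOF, GS-331007, VEL, and VOX concentration data using the respective population PK models". This derivation covers everyone in the PK Analysis Set. Individual values are an intended output; one planned table is "Individual and Summary of Population PK Model-derived PK Parameters by Treatment Group".

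The derived parameters are log-transformed and set against those of the matching US NDA population in PROC MIXED, with population group as the only fixed effect. The result is a ratio with a 90% CI, and its purpose is "to assess the difference in PK exposure between Korean subjects in this study and the overall population".

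On the data behind each value, SAP 8.1 says: "A single PK blood sample will be collected at Weeks 2, 4, 8, 12, and Early Termination (if applicable) for all subjects". SAP 3.1.4 asks only that subjects took a dose and "have at least 1 nonmissing concentration value for the corresponding analyte in plasma"; exposure analyses are further limited to subjects whose exposures were successfully derived from the model. Protocol 6.7.2.1 records the time of dosing but, in the readable text, fixes no sampling time relative to the dose.

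**The concern.** When few samples are available, an individual Bayes estimate is a compromise between the subject's own concentrations and the model's prior. Here the prior comes from the population that serves as the comparator. A Korean shift would therefore be partly removed from each Korean value before the two groups are compared. The NDA mean is not moved in the same way, because those subjects are drawn toward their own centre.

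The comparison exists to show whether Korean exposure differs. Attenuation does not create a false difference. It makes a real one look smaller, in either direction, and a reader of the table could take a ratio near 1 as stronger reassurance than the data give. SAP 8.3 refers to the two one-sided tests approach, in which closeness of the interval to 1 is what counts.

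**Working it through.** The documents give no expected ratio, variability, shrinkage or margin for this comparison, so there is no planned figure to reproduce. The check asks what the mechanism does under stated assumptions.

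**Inputs from the documents.** Up to four scheduled single samples per subject (SAP 8.1), and a minimum of one nonmissing value (SAP 3.1.4). Protocol 1.2.3 says that race was not a clinically meaningful covariate in the population PK models, so nothing readable moves the prior for Korean subjects.

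**Assumptions.** Individual Bayes estimates with NDA parameters held fixed; log-scale between-subject SD w = 0.3 to 0.5; log-scale residual SD s = 0.3 to 0.6; n samples per subject.

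**Formula (linear-Gaussian case).** The expected log shift in the estimates is the true log shift times r = w²/(w² + s²/n), and shrinkage is 1 − r. The apparent ratio is therefore (true ratio)^r.

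| n | w | s | r | 1.30 appears as | 0.70 appears as |
|---|---|---|---|---|---|
| 4 | 0.3 | 0.6 | 0.09/(0.09 + 0.09) = 0.50 | 1.14 | 0.84 |
| 4 | 0.5 | 0.3 | 0.25/(0.25 + 0.0225) = 0.92 | 1.27 | 0.72 |
| 1 | 0.3 | 0.6 | 0.09/(0.09 + 0.36) = 0.20 | 1.05 | 0.93 |
| 1 | 0.5 | 0.3 | 0.25/(0.25 + 0.09) = 0.74 | 1.21 | 0.77 |

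A true ratio of 1 gives 1^r = 1.

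**Read backwards.** An apparent ratio of 1.25 corresponds to a true ratio of 1.25^(1/0.8) = 1.32 at 20% shrinkage and 1.25^(1/0.5) = 1.56 at 50%.

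**The interval.** If r is the same in both groups, the individual estimates contract by r, so the standard error of the log ratio contracts by r along with the estimate. Whether the interval excludes 1 is then unchanged. What is lost is its value as a statement of how large a difference could be.

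**Simulation.** A one-compartment oral model with individual Bayes estimates, 400 subjects per group and assumed variability gave the same pattern. With four samples at random times, realised AUC ratios of 1.55, 1.53, 1.47 and 1.54 were estimated as 1.44, 1.30, 1.38 and 1.29 for assumed half-lives of 15 to 25 h. For an assumed half-life of 0.5 h, 1.55 and 1.51 were estimated as 1.28 and 1.17. The SD of the individual estimates was 0.23 to 0.35, against a true 0.39 to 0.40. With nine samples in a fixed profile the loss was smaller: 1.50 became 1.43 and 1.60 became 1.54.

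**Effect estimated inside the model.** In the linear-Gaussian setting with w = 0.4, s = 0.7 and n = 4, r = 0.16/(0.16 + 0.1225) = 0.57. A true ratio of 1.5 appeared as 1.26 from individual estimates and as 1.50 when the group effect was estimated directly.

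**The case against.** The strongest reply is that the premise is not written down. SAP 8.3 does not call the values Bayes estimates and does not say that the NDA parameters are held fixed. The models' covariates are not shown; if they include characteristics on which Korean subjects differ, that part of a shift is already in each subject's prior and is not shrunk. Protocol 8.6 defers details to a PK reporting and analysis plan that is not available here, and SAP 8.3 mentions a later population PK report. All of this stands, and it is why the point is conditional. It does not clear the plan. SAP 8.3 itself fixes the comparison, its code and its tables, and re-estimating on pooled data without a Korean term would still draw both groups toward a common centre.

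The sampling is also only partly visible: the models "will be applied to the data collected from CCI sparse CCI PK sampling of this study". The SAP's PK abbreviations define AUClast and a terminal rate constant, which suggests that some subjects have serial profiles. This stands too. Four samples is the readable schedule, not a documented maximum, and richer sampling would reduce the attenuation for those subjects.

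The size rests wholly on assumed variances, and the range runs from trivial (1.30 seen as 1.27) to material (1.30 seen as 1.14). That is correct.

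Finally, PK is not among the stated objectives, no equivalence margin is visible, and SAP 3.4 plans no formal testing. So no pre-set decision is biased, and the SVR12 analysis is untouched. This limits the weight of the point but does not remove it.

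A reader might also infer that a subject with one sample simply receives the NDA typical value. The assumed range does not support that: r for one sample runs from 0.20 to 0.74.

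**Conclusion.** The point holds conditionally. As far as SAP 8.3 can be read, its ratio is built so that a real Korea/NDA difference can be attenuated toward 1, with the 90% CI centred on the attenuated value, and nothing in the readable text guards against this or measures it. This requires individual Bayes estimates under essentially unmodified NDA models, material shrinkage, and a true ratio other than 1. Under the assumed variances a true 1.30 would appear as 1.14 to 1.27 with four samples and as 1.05 to 1.21 with one. The actual size is unknown and would differ by analyte and parameter.

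A reader might go further and conclude that the plan is certain to understate any Korean difference, or that it leads to a finding of no difference. The documents do not support either. The estimator is unstated, part of the sampling is redacted, and no decision rule is visible. The point is a low-cost improvement to a secondary comparison.

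**What to change.** In SAP 8.3:

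- State the individual estimator and whether the NDA parameters are fixed or re-estimated, or cite the PK plan that does.
- Add a model-based comparison per analyte. Fit the study concentrations with the NDA parameters fixed plus a Korean effect on CL/F, and on V/F or relative bioavailability where estimable.
- Report the Korea/NDA ratio of AUCtau with a 90% CI. Because CL/F is dose divided by AUC, an effect on CL/F alone gives exp(−effect), not exp(effect). Derive the Cmax and Cmin/Ctau ratios from the fitted model, each with a 90% CI.
- If the models carry other covariates, say whether the ratio is adjusted for them. An adjusted ratio answers a different question from the overall Korea/NDA difference that SAP 8.3 describes.
- Keep the PROC MIXED table as descriptive and print the shrinkage for each parameter beside it. Set a shrinkage limit in advance, and do not read a ratio near 1 as evidence of no difference where the limit is exceeded.

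The cost is SAP wording and one extra model run per analyte by the PK scientist, who is already due to prepare a population PK report. No new samples are needed. The interval will be wider than the one planned, and with the NDA parameters fixed it will not carry their uncertainty.

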1.5. Risk/Benefit Assessment for the Study

This study will provide information on the safety and efficacy of the combination of SOF/VEL FDC for 12 weeks in Korean patients that are treatment-naïve or treatment-experienced with IFN-based treatment and SOF/VEL/VOX FDC for 12 weeks in Korean patients that are treatment-experienced with NS5A DAA-based treatments.

The safety profile of SOF/VEL FDC has been established in 3,345 subjects, included in the Phase 3 studies, Phase 2 studies and Phase 1 studies which enrolled subjects with compensated and decompensated cirrhosis. No clinical safety issues specifically related to the combination of SOF/VEL FDC have been identified to date. Overall, SOF/VEL FDC for 12 weeks was safe and well tolerated in patients with or without cirrhosis.

The safety assessment of SOF/VEL/VOX FDC has been established based on data from Phase 3 clinical studies in which > 1,000 subjects received SOF/VEL/VOX FDC for 12 weeks. There were no patients receiving SOF/VEL/VOX FDC for 12 weeks who permanently discontinued treatment due to adverse reactions. Overall, SOF/VEL/VOX FDC for 12 weeks was safe and well tolerated in patients for the treatment of chronic HCV infection in adults without cirrhosis or with compensated cirrhosis who have failed prior treatment with a HCV DAA.

During the conduct of the study, the sponsor together with the investigator will perform ongoing safety reviews.

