1.2. Study Design

This is a multicenter, open-label study in approximately 80 subjects with chronic HCV infection.

Cohort 1: Approximately 50 subjects with chronic HCV infection, genotype 1 or 2, will be enrolled and treated with SOF/VEL FDC for 12 weeks. Subjects may be treatment-naïve or treatment-experienced with IFN-based treatments.

Cohort 2: Approximately 30 subjects with chronic HCV infection, genotype 1, will be enrolled and treated with SOF/VEL/VOX FDC for 12 weeks. Subjects will be treatment-experienced with NS5A DAA-based treatments.

The total time to complete all study visits is approximately 28 weeks (30 weeks for those requiring an extension to the Screening period):

- 28 days (4 weeks) screening period [up to 42 days (6 weeks) for extenuating circumstances may be granted]
- 12 weeks study treatment period
- 12 weeks posttreatment period

The schedule of assessment is provided as an appendix to the SAP ([Appendix 1](#)).

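### The Korea versus US NDA exposure comparison pools one residual variance over two groups of probably very different size, so its 90% CI keeps its level only if the log-scale SDs are equal

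*SAP*

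**What the plan says.** SAP 8.3 applies the population PK models built for the two US NDAs to this study's samples and compares the resulting parameters with the matching NDA population "to assess the difference in PK exposure between Korean subjects in this study and the overall population". The model is described in one sentence: "The statistical model will include population group as a fixed effect". The code follows. The procedure line is "proc mixed data poppk method type3" (the equals signs were lost when the PDF was read), the model line is "model logval popgrp", and the contrast of Korea with the NDA population is "popgrp 1 -1 / cl alpha 0.1". There is no `REPEATED` statement, no `GROUP=` option and no `ddfm` option.

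The limits are exponentiated to a test-to-reference ratio with a 90% CI, "which is consistent with the two 1-sided tests approach". The visible text of SAP 8.3 gives no NDA sample size, no SD, no check of equal variances and no acceptance limits.

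On group size, SAP 1.2 plans: "Approximately 50 subjects with chronic HCV infection, genotype 1 or 2, will be enrolled and treated with SOF/VEL FDC for 12 weeks". It plans about 30 for SOF/VEL/VOX. The only hint of the comparator's scale is in Protocol 1.5: "The safety profile of SOF/VEL FDC has been established in 3,345 subjects", and more than 1,000 for SOF/VEL/VOX. These are safety counts, not PK sample sizes.

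**The concern.** With one fixed effect and one residual variance, the printed code gives the ordinary pooled two-sample t interval on the log scale. Pooling is nearly harmless when the groups are of similar size. When one group is far larger, the pooled variance is essentially that group's variance, while the true standard error of the difference is driven by the smaller group's variance divided by its small n. The interval is then sized by the wrong population's spread.

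Nothing in the documents supports equal spread. One side is a single-country trial, and the other is the wider NDA population. If the Korean spread is larger, the CI is too narrow and claims more precision than the data hold. If it is smaller, the CI is too wide and can hide similarity. Tying the interval to two one-sided tests presumes that it has its nominal level.

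**Working it through.** **Inputs.** From the documents: Korean n = 50 or 30 (SAP 1.2); one residual variance and a 90% CI (SAP 8.3). Assumed, because the documents do not give them: NDA PK sample size N = 500, 1,000 or 3,000 (300 as a lower check), and Korean/NDA ratio of log-scale SDs r = 0.7 to 1.43. The NDA SD is set to 1, since only the ratio matters for coverage.

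**Formulas.**
- Pooled variance = [(n − 1)r² + (N − 1)] / (n + N − 2)
- Planned SE = √[pooled variance × (1/n + 1/N)]
- True SE = √(r²/n + 1/N)
- Coverage ≈ 2Φ(1.645 × planned SE / true SE) − 1

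**The plan's own figure.** At r = 1 the two SEs are equal and coverage is 90.0% for every n and N, so the nominal level is reproduced under equal SDs. With equal group sizes (50/50 or 30/30) it also stays at about 90% for every r tried.

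**Where the pooled variance comes from.** For n = 50 and N = 1,000, the Korean group supplies 49/1,048 = 4.7% of the degrees of freedom. With equal SDs it supplies 0.020/0.021 = 95% of the true variance of the difference.

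**Worked case, r = 1.25, n = 50, N = 1,000.**
- Pooled variance = (49 × 1.5625 + 999)/1,048 = 1.026
- Planned SE = √(1.026 × 0.021) = 0.147
- True SE = √(0.03125 + 0.001) = 0.180
- SE ratio = 0.817, so coverage = 2Φ(1.344) − 1 = 82.1%

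**Worked case, r = 0.8, same n and N.**
- Pooled variance = (49 × 0.64 + 999)/1,048 = 0.983
- Planned SE = 0.144; true SE = √(0.0128 + 0.001) = 0.117
- SE ratio = 1.223, so coverage = 95.6%

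**Coverage (%) of the planned nominal 90% CI.**

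| Korean n | NDA N | r = 0.7 | 0.8 | 1 | 1.25 | 1.43 |
|---|---|---|---|---|---|---|
| 50 | 500 | 97 | 95 | 90 | 83 | 78 |
| 50 | 1,000 | 98 | 96 | 90 | 82 | 77 |
| 50 | 3,000 | 98 | 96 | 90 | 82 | 76 |
| 30 | 500 | 98 | 95 | 90 | 82 | 77 |
| 30 | 1,000 | 98 | 96 | 90 | 82 | 76 |
| 30 | 3,000 | 98 | 96 | 90 | 81 | 75 |

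At N = 300, a ratio of 1.25 still gives about 83–84%. Simulation with 400,000 draws per setting, for r from 0.67 to 1.5, agrees with the formula. In the same runs the separate-variance interval with Satterthwaite degrees of freedom covers 89.9–90.1% in every setting.

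**On the ratio scale** (NDA log SD 0.4 assumed, N = 1,000, true ratio 1):

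| Korean n | r | Pooled 90% CI | Separate-variance 90% CI |
|---|---|---|---|
| 50 | 1.25 | 0.908–1.102 | 0.887–1.128 |
| 50 | 0.8 | 0.910–1.099 | 0.924–1.082 |
| 30 | 1.25 | 0.884–1.131 | 0.855–1.169 |
| 30 | 0.8 | 0.886–1.129 | 0.904–1.107 |

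**The case against.** The strongest reply is that no error has been shown in this trial. Neither SD is given, the NDA PK sample size is not given, and at equal SDs the planned interval is right. That stands: the point is conditional.

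The direction is also open. A reader might infer from the 75–78% figures that the CI is too narrow. The documents do not support that. A single-country sample, sparse sampling and shrinkage toward a model built on other data could all make the Korean spread smaller, and the CI would then be too wide, which is the cautious side for a claim of similarity.

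A reader might also take this CI for the sole inferential PK output, or for a decision rule. That cannot be established. SAP 8.2 is redacted, Protocol 8.6 refers the details to a separate PK reporting and analysis plan, and SAP 8.3 announces a separate population PK report. PK is not among the study objectives or the listed primary and secondary endpoints.

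Pooling also buys a more stable width. With equal SDs and N = 1,000, the separate-variance interval is on average about 1% (n = 50) or 2% (n = 30) wider. The coefficient of variation of its half-width is about 10% or 13%, against about 2% for the pooled interval.

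Finally, the calculations treat the parameters as independent normal values on the log scale. The real inputs are model-derived, and neither interval carries the uncertainty of the PK model. The 90% level after the change is therefore shown for the idealised case only.

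What remains is that the printed code is fully visible, it pools, and nothing visible checks or relaxes the equal-variance assumption.

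**Conclusion.** The concern holds as a conditional weakness. If the NDA PK population is much larger than 30 or 50, the planned 90% CI reflects the NDA spread and misses its nominal level when the log-scale SDs differ. For an assumed N of 500 to 3,000, coverage runs from about 75–78% (SD ratio 1.43) and 81–83% (1.25) to 95–96% (0.8) and 97–98% (0.7).

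The documents do not support the stronger conclusion that the interval is wrong in this trial, or wrong in a known direction. The consequence is modest: the estimated ratio does not change, SAP 8.3 sets no acceptance limits, and SVR12 is untouched. In the illustration at an SD ratio of 1.25, each limit moves by 0.02 to 0.04. This is a cheap improvement to a secondary comparison.

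**What to change.** In the SAP 8.3 code, replace `method=type3` with `method=reml`, add `repeated / group=popgrp;`, and put `ddfm=satterthwaite` on the MODEL statement. Keep the ESTIMATE statement and the 90% CI. Add one sentence stating that the residual variance is estimated separately by population group, and report n and the log-scale SD of each group for every parameter. The pooled interval may be shown beside the new one.

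The cost is a few code edits and one SAP sentence, with no new data. The statistical price is the small increase in mean width and the less stable width that arise if the two SDs are in fact equal.
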